9. EFFICACY ANALYSES

9.1 Continuous Outcomes

The mean change from each baseline in the continuous outcome of interest will be analyzed using a restricted maximum likelihood (REML) based repeated measures approach, without imputation. The model will include all participants in the safety population. The dependent variable will be the observed change from baseline each in outcome at each post-randomization visit.

9.1.1 Efficacy Analysis Model

Continuous endpoints collected at baseline and Week 12 will be analyzed in an analysis of covariance model (ANCOVA) for the change from each baseline (P301 baseline and P303 baseline) in separate, independent models. The model will include all participants in the safety population, and the dependent variable will be the observed change from each baseline to Week 12. Covariates in the model will include the fixed categorical effects of treatment, site, sex, current tobacco use status, presence of current MDE, as well as the continuous fixed covariate of baseline score.

The least squares means and 95% confidence intervals (CIs) will be calculated for the treatment difference between the subjects that received TNX-102 SL and placebo in the lead-in study at each time point.

Endpoints reported in this manner will include:

- CAPS-5 Total Score
- Change from baseline in SDS total.
- Change from baseline in participants' quality of sleep using the PROMIS Sleep Disturbance scale.
- Change from baseline in the disruption of work/school activities assessed using the SDS.
- Change from baseline in disruption of social life/ leisure activities assessed using the SDS.
- Change from baseline in the disruption of family life/home responsibilities assessed using the SDS.
- Change from baseline in CAPS-5 Arousal and Reactivity (Criterion E).
- Change from baseline in CAPS-5 Intrusion symptoms (Criterion B).
- Change from baseline in CAPS-5 Negative Cognition and Mood (Criterion D).
- Change from baseline in CAPS-5 Persistent Avoidance (Criterion C).
- Change from baseline in CAPS-5 Sleep Disturbance (item E-6).
- Change from baseline in CAPS-5 Exaggerated Startle (item E-4).
- Change from baseline in CAPS-5 Reckless or Self-Destructive Behavior (item E-2).
- Change from baseline in CAPS-5 Depersonalization (item 29).
- Change from baseline in CAPS-5 Derealization (item 30).

The change from baseline in BDI-II score will be analyzed in a Mixed Model Repeated Measures (MMRM) for the change from each baseline (P301 baseline and P303 baseline)

in separate, independent models. The model will include all participants in the safety population, and the dependent variable will be the observed change from each baseline at each post-randomization visit. Covariates in the model will include the fixed categorical effects of treatment, site, sex, current tobacco use status, presence of current MDE, visit and treatment by visit interaction, as well as the continuous fixed covariates of baseline score and baseline score by visit interaction. An unstructured covariance matrix will be used to model the within-subject variance-covariance errors. The Kenward-Roger approximation will be used to estimate the denominator degrees of freedom. Should the unstructured model fail to converge, an autoregressive AR(1) covariance structure will be attempted, then finally compound symmetric should AR(1) not converge.

The least squares means and 95% confidence intervals (CIs) will be calculated for the treatment difference between the subjects that received TNX-102 SL and placebo in the lead-in study at each time point.

CGI-I score (which does not have baseline assessments) will use the same method, however, the observed baseline response and associated interactions removed from the list of covariates. All visits will be included in the analysis. P-values from these comparisons will be considered nominal.

For each outcome, descriptive statistics (mean, SD, median, minimum and maximum) will be reported as well as LS means, standard error (SE) and p-values comparing the arms at each visit. In addition, for the SDS, the frequency of participants not working or attending school due to reasons unrelated to PTSD will be reported overall and within each visit.

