12. STATISTICS

A complete description of the statistical analyses to be performed will be provided in a statistical analysis plan (SAP), which will be finalized prior to database lock. Two baselines for analysis are defined:

1. Baseline 1: the original baseline randomization scores from the lead-in study.
2. Baseline 2: baseline scores from Visit 1 of this study, which will be the same scores as the final endpoint efficacy scores from the Week 12, final primary outcome visit from the lead-in study.

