3.2 Method of Treatment Assignment and Randomization

All patients will be assigned to TNX-102 SL, 5.6 mg regardless of which treatment arm they were randomized to in the lead-in study. No patients or site personnel will know what the prior treatment was in the double-blind lead-in study.

Throughout this document, when describing analyses performed by treatment group, this will refer to the treatment that the subject was randomized to in the double-blind lead-in study.

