7. GENERAL ISSUES FOR STATISTICAL ANALYSIS

7.1 General Statistical Methodology

Descriptive summaries will be provided where appropriate for each of the primary and secondary variables. In general, tables will summarize data by treatment group that the subjects were randomized to in the prior study and visit.

All tables will be completed for the Safety Population unless otherwise specified

Continuous, quantitative, variable summaries will include the number of participants (N) with non-missing values, mean, standard deviation (SD), median, minimum, and maximum.

Categorical, qualitative, variable summaries will include the frequency and percentage of participants who are in the particular category. In general, the denominator for the percentage calculation will be based upon the total number of participants in the study population for the treatment group unless otherwise specified.

Two baselines will be utilized for most analyses: P301 baseline values are defined as the last non-missing measurement prior to the first dose of double-blind study drug in study P301; likewise, P303 baseline values are defined as the last non-missing measurement prior to the first dose of open-label study drug in study P303. Change from baseline will be defined as the post-baseline visit value minus the baseline value and will be calculated for both baselines.

ET participants will only be followed if required to monitor an on-going adverse event or other condition.

Participants are not supposed to change study sites; however, should this be necessary to allow a participant to continue in the study, participants will be analyzed under the site where they were initially enrolled.

Study day after first dose is defined as assessment date – first dose date +1. Dates prior to first dose are defined as assessment date – first dose date. Note that the protocol refers to “Day 0”; for the purposes of the datasets and analyses, this would appear as day 1.

All analyses will be performed using Statistical Analysis System (SAS[®]) Software version 9.4 or later.

Unless otherwise noted, 95% confidence intervals will be presented for statistical tests.

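### Does adjusting for the P303 baseline, which the lead-in treatment may already have shifted, spoil the comparison of lead-in arms in the extension?

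*SAP*

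**What the plan says.** SAP 9.1.1 fits an ANCOVA to change at Week 12 for 15 listed endpoints: CAPS-5 total, clusters and items, SDS total and domains, and PROMIS sleep. It does so "for the change from each baseline (P301 baseline and P303 baseline) in separate, independent models". Covariates are treatment, site, sex, tobacco use and current MDE, "as well as the continuous fixed covariate of baseline score". BDI-II has an MMRM of the same form, "as well as the continuous fixed covariates of baseline score and baseline score by visit interaction". The SAP does not spell out which baseline score enters which model.

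The effect estimated is "the treatment difference between the subjects that received TNX-102 SL and placebo in the lead-in study at each time point". SAP 3.2 confirms that for analyses by treatment group "this will refer to the treatment that the subject was randomized to in the double-blind lead-in study"; everyone takes TNX-102 SL in the extension.

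Under SAP 7.1, "P303 baseline values are defined as the last non-missing measurement prior to the first dose of open-label study drug in study P303". Protocol 12 describes the same quantity as "baseline scores from Visit 1 of this study, which will be the same scores as the final endpoint efficacy scores" of the lead-in study. Protocol 9.1.2 has assessments repeated if more than 14 days pass, but the repeated value also follows randomised treatment.

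For each outcome, SAP 9.1.1 says "descriptive statistics (mean, SD, median, minimum and maximum) will be reported as well as LS means, standard error (SE) and p-values comparing the arms". Protocol 12.2 also displays change from both baselines by lead-in arm.

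**The concern.** A baseline covariate is normally measured before randomisation, so the compared treatment cannot affect it. Only the P301 score meets that condition here. If TNX-102 SL worked in the lead-in, the arms enter P303 at different levels, and adjusting for that level changes the question. It is no longer whether the arms changed by different amounts. It is whether patients with the same P303 baseline score, but different lead-in treatment, end at different scores.

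A natural question for an extension is whether former placebo patients catch up after switching. On that question the adjusted contrast can mislead an unwary reader: it can favour TNX/TNX when neither group's mean moved, or show only part of a full catch-up. The table would set mean changes next to LS means that disagree with them, without explanation. The 15 ANCOVA endpoints and BDI-II are exposed. The models of change from the P301 baseline, and CGI-I (which has no baseline covariate), are not.

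**Working it through.** **Inputs.** The structure comes from SAP 3.2, 7.1 and 9.1.1. Neither document gives an SD, group size, lead-in effect or correlation (Protocol 12.3 and SAP 5 make no sample size calculation), so there is no planned figure to reproduce. Assumed for illustration: SD 12, 80 entrants per group, b = 0.5 to 0.8, correlation 0.5 between P301 and P303 scores, 2,000 simulated trials per setting.

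**Identity.** Write contrasts as TNX/TNX minus Placebo/TNX, with negative values favouring TNX/TNX. Let D be the entrants' difference at P303 baseline in favour of TNX-102 SL. The model for change is a + τ·arm + (b−1)·P303 score. Taking the difference between arm means gives raw difference = τ + (1−b)D, so

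τ = raw difference − (1−b)D.

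The two agree only if D = 0 or b = 1. This is exact for an ANCOVA with treatment and baseline score alone.

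**Neither arm's mean changes, no selection into P303.** The raw difference is 0, so τ = −(1−b)D:

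| D | b = 0.5: formula (simulated) | b = 0.7 | b = 0.8 |
|---|---|---|---|
| 2 | −1.0 (−1.06) | −0.6 (−0.60) | −0.4 (−0.41) |
| 4 | −2.0 (−2.02) | −1.2 (−1.18) | −0.8 (−0.80) |
| 6 | −3.0 (−3.00) | −1.8 (−1.82) | −1.2 (−1.17) |

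Using the P301 score as covariate for the same change gives −0.09 to 0.04; the raw difference is −0.10 to 0.03.

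**Full placebo catch-up, D = 4.** The raw difference is 4. τ = 4 − 0.5×4 = 2.0 at b = 0.5, and 4 − 0.2×4 = 3.2 at b = 0.8. The simulated range is 1.90 to 3.20. With the P301 covariate it is 3.88 to 4.00.

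**Selected entry.** Entry to P303 depends on completion, compliance, clinical stability and consent (Protocol 7.2, 12.3). Suppose the worst lead-in Week 12 scorers stay out, and let L be the arm difference among all completers. With b = 0.5 and no mean change:

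- L = 0, non-entry 30% placebo and 15% TNX-102 SL: D = −2.66, raw −1.38, so τ = −1.38 − 0.5×(−2.66) = −0.05. With the P301 covariate: −1.17. Here the raw and P301-adjusted figures carry the spurious advantage, and the SAP's contrast does not.
- L = 4, non-entry 20% and 15%: D = 3.16, raw −0.36, so τ = −0.36 − 0.5×3.16 = −1.94. With the P301 covariate: −0.29.
- At L = 2, 4 and 6 the P303-adjusted contrast is −1.06, −2.02, −3.00 without selection; −1.07, −1.94, −3.07 with 20%/15%; and −1.02, −1.99, −3.01 with 30%/15%. It hardly moves, because selection on a covariate leaves the regression given that covariate intact. It tracks −(1−b)L, so it is the completers' difference L that moves it away from zero; D fixes only its distance from the raw figure.

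**Other covariates.** With about 35 sites (Protocol 6.1), three binary covariates of no effect, b = 0.5 and D averaging zero, the P303-adjusted contrast still departs from the raw difference with a trial-to-trial SD of about 1.35. For the P301-change model the SD is about 1.7. These gaps are random and centred on zero, unlike (1−b)D, but they show that LS and raw differences part company in every adjusted model here.

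**The case for a change.** The best case for a change is that the SAP neither names the covariate nor says what the P303-change contrast means, while the discrepancy is systematic and foreseeable. An effective drug makes D non-zero. Under no mean change and no selection, with L = 2 to 6, the P303-adjusted contrast reached nominal p < 0.05 in 6% to 41% of simulated trials, against 4% to 6% with the P301 covariate. A second contrast adjusted for the P301 score would use data already in hand. Its standard error ran from 2% narrower to 12% wider.

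The algebra stands, and so does the point that a reader should know the contrast is conditional. The rest carries less weight. The 6% to 41% counts as error only if difference in mean change is the target; for the conditional question those are real differences. The P301-adjusted contrast almost repeats the difference in mean changes already on display, so it adds little beyond an interval and a p-value. It would also bring 15 + 3 = 18 further unadjusted contrasts (15 ANCOVA endpoints, and BDI-II at three visits). When non-entry differs strongly by arm and the lead-in effect is small, it is the more biased of the two. Entry driven by factors other than the Week 12 score can bias all three estimates, so none is a safe reference.

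**Conclusion.** No change to the plan. Whether to compare arms by mean change or conditionally on the score at entry is a choice on which competent statisticians differ, and adjusting a change score for its own baseline is the ordinary one. The unnamed covariate is a gap an analyst fills without difficulty: two separate models, one per baseline, each with its own baseline score. A reader who wants the unconditional picture has mean change by arm from both baselines, and the planned P301-baseline models, which condition on no post-randomisation score.

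The gap would be 0.4 to 3.0 points for D between 2 and 6 and b between 0.5 and 0.8, and zero if the entrants' arms do not differ. Those values are assumptions, and the exact formula ignores the site, sex, tobacco and MDE terms and the MMRM's visit structure. The consequence is limited to interpretation: safety is the primary objective (Protocol 5.1), the CAPS-5 comparison of lead-in arms is exploratory (Protocol 12.5), and all p-values are nominal (SAP 7.1.1.1). How the contrast is described is a matter for the study report.

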3. OVERALL STUDY DESIGN AND PLAN

This is a 12-week, multicenter, open-label extension study designed to accumulate additional safety exposure and efficacy data with daily bedtime dosing of TNX-102 SL 5.6 mg (2 x 2.8mg tablets) in patients with PTSD. This study will be conducted at approximately 35 sites in the United States (US).

Patients who have completed participation in a Phase 3, randomized, double-blind, placebo controlled study comparing TNX-102 SL 5.6 mg versus placebo for the treatment of PTSD will be eligible. This extension study consists of 5 visits, including the Screening/Baseline visit (which is anticipated to be the same as the primary outcome visit in the double-blind lead-in study), a telephonic visit at week 2, and in-clinic visits after 4, 8 and 12 weeks of treatment (Visits 3-5). The total treatment duration of this study will be 12 weeks. Therefore, the maximum total duration of continuous treatment with TNX-102 SL could be approximately 24 weeks for those patients assigned to active study drug in the lead-in study.

Patient data collected at the Week 12 visit in the lead-in study will be used as one of the defined baselines for this study. There is no need to repeat assessments at Visit 1 for this study, if they were collected in the lead-in study and patients enroll and initiate study treatment within fourteen days of completing the lead-in study. After the patient has completed his/her participation in the lead-in study and has consented to participate in this open-label extension study, patients will be dispensed a 4-week supply of open-label TNX-102 SL tablets and will be instructed to take the study drug sublingually daily at bedtime, starting on the evening of Visit 1. A phone visit will be completed after 2 weeks of treatment and patients will return to the study center for safety and efficacy assessments at Weeks 4, 8, and 12 (or early termination). At the Weeks 4 and 8 visits patients will return their TNX-102 SL medication and will receive another 4-week supply. Patients will be allowed to take medications deemed appropriate by their health care providers to manage their PTSD and other conditions, including currently approved PTSD therapies.

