5. SAMPLE SIZE DETERMINATION

No sample size calculations were made for this study as it is a follow-on, open-label study. The sample size for this study will depend upon the number of patients who complete the lead-in study, remain eligible for entry, and indicate willingness to participate in this extension study.

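### SAP 9.1.1 fits about 35 sites as unpooled fixed effects in every continuous-outcome model; one-arm sites then add nothing to the ANCOVA contrast, and its CIs are wider than they need be

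*SAP*

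**What the plan says.** SAP 9.1.1 lists 15 endpoints measured at baseline and Week 12 and analyses each by ANCOVA, separately against the P301 and P303 baselines. The model terms are given as: "Covariates in the model will include the fixed categorical effects of treatment, site, sex, current tobacco use status". Current MDE status and the baseline score complete the list. BDI-II goes into an MMRM with the same categorical terms, including site, extended by: "presence of current MDE, visit and treatment by visit interaction, as well as the continuous fixed covariates of baseline score and baseline score by visit" (the last term is again an interaction). Site is a main effect there, with no site-by-visit term. For the remaining continuous outcome, "CGI-I score (which does not have baseline assessments) will use the same method", without the baseline terms, so site stays in.

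The responder analyses in SAP 9.1.2 are different. They use a CMH test stratified by current MDE only, and site plays no part.

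On scale, SAP 3 says: "This study will be conducted at approximately 35 sites in the United States (US"). On numbers, SAP 5 says: "No sample size calculations were made for this study as it is a follow-on, open-label study". It then gives what determines enrolment: "The sample size for this study will depend upon the number of patients who complete the lead-in study, remain eligible for entry". Willingness to take part is the remaining condition.

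The only rule on site handling is in SAP 7.1: a patient who moves is analysed under the enrolling site. Neither document gives a minimum site size, a pooling rule or a random-site alternative. The convergence fallback in SAP 9.1.1 changes the covariance structure, not the site term.

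**The concern.** Enrolment is limited to lead-in completers who qualify and agree to continue, so some of about 35 sites may supply only a few patients. Week 12 data thin these further: continuous outcomes are not imputed, and SAP 7.1.2 assigns an early-termination visit to its nearest window, which may not be Week 12.

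When each site has its own fixed parameter, the arm contrast is estimated only from differences within sites. A site with patients from one arm offers no such difference. Its patients are in the database but do not inform the contrast in the ANCOVA. That contrast covers change in total CAPS-5, which SAP 7.2.1 calls the primary efficacy endpoint and for which Protocol 12.5 plans a lead-in arm comparison. What is at stake is the width of the intervals around the LS mean differences. There is also a practical risk that, with no rule in place, small sites are pooled ad hoc once the data are visible.

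**Working it through.** **Inputs from the documents.** About 35 sites (SAP 3); no planned N (SAP 5); site as a fixed effect (SAP 9.1.1); 95% intervals (SAP 7.1). The plan states no N, SD, allocation ratio or site variance, so there is no figure of its own to reproduce.

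**Assumptions.** N from 50 to 250; lead-in arms 1:1 and not blocked by site; 35 sites with uneven enrolment (exponential weights) or equal enrolment; no true site variance unless stated.

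**Step 1: weight of a site in the ANCOVA.** With site fixed, and ignoring the other covariates,

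Var(contrast) = σ² / W, where W = Σ over sites of n1·n0/(n1+n0).

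- One-arm site: n1·0/(n1+0) = 0.
- One patient per arm: 1·1/2 = 0.5.
- Two per arm: 2·2/4 = 1.

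**Step 2: direct check on design matrices.** Fifteen sites with two patients per arm give W = 15 and variance 1/15 = 0.0667σ².

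- Adding 20 one-patient sites to the ANCOVA leaves it at 0.0667.
- Adding instead 10 sites with one patient per arm gives W = 15 + 10×0.5 = 20, so 1/20 = 0.050 (0.0502 with a baseline covariate fitted). Small two-arm sites therefore count.
- In the MMRM (three visits, assumed within-patient correlation 0.6), the 20 one-patient sites cut the Week 12 contrast variance from 0.0667 to 0.0622, a fall of 0.0045/0.0667, or about 7%. Because site is a main effect only, within-patient change still carries information.

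**Step 3: loss of precision with uneven sites.** Let I be the within-site sum of squares of the arm indicator divided by its total. Relative to a model without site, CI width is about 1/√I before the loss of residual degrees of freedom. The pooled columns combine sites with fewer than 2 patients in either arm.

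| N | I, unpooled | 1/√I | I, pooled | 1/√I |
|---|---|---|---|---|
| 80 | 0.702 | 1.19 | 0.964 | 1.02 |
| 100 | 0.745 | 1.16 | 0.956 | 1.02 |
| 150 | 0.815 | 1.11 | 0.945 | 1.03 |
| 200 | 0.855 | 1.08 | 0.944 | 1.03 |
| 250 | 0.880 | 1.07 | 0.944 | 1.03 |

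At N=100 about 26 sites are non-empty. Residual df are 100−26−1−4 = 69, against 100−2−4 = 94 without site. The t quantiles are 1.995 and 1.986, a further factor of about 1.005. Averaged over simulations with the df loss included, the unpooled ratio is 1.17 at N=100 and 1.07 at N=250.

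**Step 4: sensitivity to the assumptions.** CI width relative to no site term, df loss included, with the share of patients at one-arm sites:

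| N | Uneven: unpooled | One-arm sites pooled | Patients at one-arm sites | Equal: unpooled | One-arm sites pooled | Patients at one-arm sites |
|---|---|---|---|---|---|---|
| 50 | 1.34 | 1.06 | 35% | 1.54 | 1.04 | 49% |
| 100 | 1.17 | 1.06 | 17% | 1.23 | 1.06 | 24% |
| 150 | 1.11 | 1.06 | 10% | 1.14 | 1.07 | 12% |
| 250 | 1.07 | 1.04 | 5% | 1.08 | 1.07 | 3% |

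**Step 5: when sites truly differ.** With uneven sites, 1:1 arms, N from 80 to 250 and site explaining 0–20% of outcome variance, the pooled CI (fewer-than-2 rule) was narrower than the unpooled CI in every scenario, with coverage about 95%. At N=100 with no site variance, the half-width was 0.407 against 0.463 SD (1 − 0.407/0.463 = 12% narrower). At N=250 with 20% site variance, it was 0.233 against 0.238 SD (about 2% narrower).

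**The case against.** The strongest reply is that removing site differences is the reason for fitting site, and a calculation with no site variance leaves that benefit out. This is fair as far as it goes. Compared with dropping site altogether, the unpooled term pays for itself once site explains more than about 26% of variance (uneven sites) or 33% (equal sites) at N=100, and 12% or 14% at N=250. But the proposal is to pool, not to drop site, and pooling kept an advantage up to 20% site variance, although a small one at N=250.

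A second reply is that N, site sizes and allocation are all assumed. That stands. The lead-in randomisation scheme is not in these documents, and blocking by site would reduce the number of one-arm sites.

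A third is that little depends on the contrast. Safety is the primary objective and its planned summaries contain no site term, efficacy is secondary in the protocol, p-values are nominal, and no power is claimed. This also stands and limits the importance of the point.

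A reader might go further and infer that all small sites are wasted, that patients at one-arm sites are wholly discarded, or that every efficacy analysis is affected. The documents do not support these readings. A site with one patient per arm has weight 0.5. A one-arm site with two or more patients still informs the residual variance and covariate slopes. The MMRM gains a little even from one-patient sites. The CMH analyses do not use site.

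**Conclusion.** The point holds as a matter of precision. In the ANCOVA, one-arm sites have exactly zero weight in the lead-in arm contrast, and the SAP has no rule to deal with them. Under 1:1 arms, uneven sites and no site variance, the CI is about 17% wider than without site at N=100 and about 7% wider at N=250; pooling sites with fewer than 2 patients in either arm reduces this to about 2–3%. The cost is larger if N is near 50 and shrinks as N or site variance rises. These widths are for the ANCOVA and should not be carried over to the MMRM, where one-arm sites keep some information.

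It would be wrong to conclude that the planned analysis is biased or its intervals invalid. Under the stated model the unpooled contrast is unbiased and the CIs keep their coverage. This is a low-priority improvement, worth making because it is cheap.

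**What to change.** Add to SAP 9.1.1: before database lock and without reference to outcomes, a statistician with access to the lead-in assignments will combine into one pooled site all sites that have, in either lead-in arm, fewer than 2 safety-population participants with any post-baseline efficacy data. The resulting pooled-site factor replaces site in all ANCOVA and MMRM models. Sites and patients stay blinded to lead-in treatment. Report the number of one-arm sites and of pooled sites.

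Basing the count on any post-baseline efficacy data gives one factor for all endpoints. A retained site could still be one-arm for a particular Week 12 endpoint, which is an acceptable price for a single definition.

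A milder option is to pool one-arm sites only. It leaves the CI about 6% wider than without site at N=100 and about 4% wider at N=250 (uneven sites), but keeps adjustment for every two-arm site.

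The cost is one sentence. The downside is that differences among the pooled sites are no longer removed, and at small N the fewer-than-2 rule pools a large share of patients: about 43% at N=100 under the assumptions above (17% from one-arm sites and 26% from small two-arm sites).

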12.2. Evaluation of Efficacy

Missing values will not be imputed, and no adjustments will be made for multiplicity in this extension study. Descriptive statistics (n, mean, SD, standard error of the mean, median, minimum, and maximum) will be displayed by the treatment received in the double-blind lead-in study and for all patients in the current study for the following efficacy parameters:

- Change from both baselines in the total CAPS-5 score
- Proportion of patients with a CGI-I score of “very much improved” or “much improved” from both baselines
- Change from both baselines in the SDS total score

- Change from both baselines in the individual items assessed by the SDS
- Change from both baselines in patients' quality of sleep using the PROMIS Sleep Disturbance scale
- Change from both baselines in CAPS-5 symptom cluster subscores
- Proportion of patients with a $\geq 50\%$ improvement from baseline (both baselines) in total CAPS-5 score
- Change from both baselines in BDI-II score

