2.2 Study Endpoints

2.2.1 Efficacy Endpoints

Comparisons will be made at each study week of data collection to both the baseline of this study (P303) and the baseline from the double-blind study (P301) and described in [section 7.1](#).

Efficacy endpoints include:

- Change from both baselines in the total CAPS-5 score
- Proportion of patients with a CGI-I score of “very much improved” or “much improved”
- from both baselines
- Change from both baselines in the SDS total score
- Change from both baselines in the individual items assessed using the SDS
- Change from both baselines in patients’ quality of sleep using the PROMIS Sleep Disturbance scale
- Change from both baselines in CAPS-5 symptom cluster subscores
- Proportion of patients with a $\geq 50\%$ improvement from baseline (both baselines) in total
- CAPS-5 score
- Change from both baselines in BDI-II score

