8. STUDY PARTICIPANTS AND DEMOGRAPHICS

8.1 Disposition of Participants and Withdrawals

The numbers and percentage of participants entering, completing the study, and withdrawing from the study, along with reasons for withdrawal, will be tabulated overall and by treatment group. This summary will be based on all participants who have data entered into the database.

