9.1.2 Categorical outcomes

Binary data over time will be analyzed using a Cochran Mantel Haenszel (CMH) test stratified by presence of current major depressive episode. Participants with missing data will be analyzed as though they are non-responders. This will be reported for each endpoint. Differences in proportions along with two-sided 95% CIs will also be reported. Two-sided p-values for the test of no difference between the treatment groups will be provided.

These endpoints will include:

- Proportion of participants with a CGI-I score of “much improved” or “very much improved”.
- Proportion of participants with a $\geq 50\%$ improvement from baseline in Total CAPS-5 score.

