12. CHANGES FROM PLANNED ANALYSIS

Study day as it appears in data listings and the Study Data Tabulation Model (SDTM) and Analysis Data Model (ADaM) datasets will differ from the protocol: The protocol describes the day of first dose as "Day 0"; the listings and datasets will conform to the standard of first dose day appearing as "Day 1".

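### The SAP plans no all-patients efficacy summary, commits to no interval for the 12-week open-label change, and contradicts itself on how many baselines the CGI-I is rated against

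*SAP*

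**What the plan says.** **Summaries.** Protocol 12.2 asks for efficacy descriptives "displayed by the treatment received in the double-blind lead-in study and for all patients in the current study". Under SAP 7.1, in general, "tables will summarize data by treatment group that the subjects were randomized to in the prior study and visit". SAP 9.1.1–9.1.2 add no pooled efficacy summary. For disposition, SAP 8.1 says that numbers "will be tabulated overall and by treatment group". The only item in SAP 12 begins "Study day as it appears in data listings" and concerns day numbering.

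**Inference.** SAP 2.2.1 promises: "Comparisons will be made at each study week of data collection to both the baseline of this study (P303") and to the lead-in baseline. In SAP 9.1.1 the least squares means and 95% CIs are "calculated for the treatment difference between the subjects that received TNX-102 SL and placebo in the lead-in study at each time point", and each outcome also gets descriptives with "LS means, standard error (SE) and p-values comparing the arms at each visit". For responders, SAP 9.1.2 says: "Differences in proportions along with two-sided 95% CIs will also be reported". Its p-values also compare the groups.

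**CGI-I.** SAP 7.2.2 poses one question, about status since treatment began at Visit 2. SAP 2.2.1 lists CGI-I response against both baselines. Protocol 10.2.2 defines the rating in two ways, and Protocol 9.3–9.5 collect both.

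**Objective.** Protocol 5.2 states the secondary objective as efficacy over the additional 12 weeks. SAP 2.1.2 states it as safety.

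**The concern.** Everyone in P303 takes TNX-102 SL. The protocol's secondary question is therefore how the efficacy measures behave over 12 more weeks on drug, for the whole cohort and by lead-in treatment. Followed as written, the SAP would omit the pooled summary that Protocol 12.2 requires. Its stated inference would go to a comparison that answers something else.

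The CGI-I problem affects what the numbers mean. If the analysis follows SAP 7.2.2, only one rating is modelled. For patients who came from placebo, a rating since lead-in treatment start combines response during the placebo period with response during open-label treatment.

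**Working it through.** The documents give no sample size, SD or expected change, so there is no figure of the plan's to reproduce and no size in scale points is claimed.

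**1. Is a pooled efficacy summary planned?**
- Protocol 12.2: by lead-in treatment, and for all patients.
- Protocol 6.3.2 and the synopsis: by treatment group and visit, with no mention of all patients.
- SAP 7.1 and 9.1.1–9.1.2: by lead-in arm. The one use of an overall figure in SAP 9 is the frequency of patients not working or attending school on the SDS, which is not a listed efficacy endpoint.
- SAP 8.1 shows that the SAP names a pooled result where it means one. SAP 12 declares no departure.

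The summary in Protocol 12.2 is therefore unplanned and its omission undeclared.

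**2. What do the stated intervals estimate?** Let m_T and m_P be the mean changes in the prior TNX-102 SL and prior placebo groups, with n_T and n_P patients and N = n_T + n_P.
- Planned contrast: D = m_T − m_P.
- Change in the cohort: M = (n_T·m_T + n_P·m_P)/N.

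If every patient's change is c points larger, D becomes (m_T + c) − (m_P + c) = D, while M becomes M + c. So D carries no information on the common change. From the P301 baseline, D is informative about early versus delayed start. From the P303 baseline it compares further change between the groups. Neither is the 12-week change.

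SAP 7.1 attaches 95% CIs to statistical tests, and the efficacy tests in 9.1.1–9.1.2 are all between prior arms. By contrast, SAP 10.2 and 10.4 do specify 95% CIs for change from each baseline in laboratory values and vital signs.

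**3. Can the missing interval be recovered?** Yes, unadjusted, from each arm's n, mean and SD (s):
- within an arm: m ± t(n−1)·s/√n
- overall: S² = [(n_T−1)s_T² + (n_P−1)s_P² + n_T(m_T−M)² + n_P(m_P−M)²]/(N−1), then M ± t(N−1)·S/√N

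Responder intervals follow from the counts.

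**4. What would a single CGI-I anchor cover?** In P303, Visit 2 is the Week 2 telephone call (Protocol 9.2) and Week 12 is Visit 5 (Protocol 9.4). SAP 7.2.1, 7.2.3 and 7.2.4.1 place Week 12 at Visit 6, so the SAP's Visit 2 appears to be lead-in numbering; that is an inference. Suppose the anchor is lead-in treatment start and P303 Visit 1 falls on the lead-in Week 12 visit. A prior-placebo patient's rating then spans:
- P303 Week 4: 12 + 4 = 16 weeks, of which 12/16 = 75% on placebo
- P303 Week 8: 12 + 8 = 20 weeks, 12/20 = 60%
- P303 Week 12: 12 + 12 = 24 weeks, 12/24 = 50%

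SAP 9.1.1 gives the CGI-I score the BDI-II method, which could mean one model per baseline, but 7.2.2 defines only one rating to put in it. SAP 9.1.2 names no baseline for CGI-I response.

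**The case against.** **No protocol text requires a CI for change.** This stands. Protocol 12.2 lists descriptive statistics only. SAP 14.1.2 allows 95% CIs where appropriate, and step 3 above shows that unadjusted intervals can be rebuilt. A reader might infer that the SAP breaches the protocol on intervals, or that the information is lost; neither is so. What remains is that the SAP permits these intervals without committing to them.

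**The protocol is not uniform on the pooled summary.** This also stands: Protocol 6.3.2 and the synopsis mention only treatment groups, and SAP 7.1 speaks only in general terms, which does not forbid a pooled column. But Protocol 12.2 is the dedicated efficacy-analysis section and is explicit, and nothing in the SAP delivers what it asks for.

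**The prior-arm comparison is legitimate.** Agreed. Protocol 6.3.2 foresees hypothesis tests on these endpoints without naming a contrast, and Protocol 12.5 plans the comparison for CAPS-5 as exploratory. It should stay. The point is that it is the only efficacy inference stated.

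**The SAP keeps both CGI-I baselines.** SAP 2.2.1 does. A reader might infer from 7.2.2 that the second baseline was dropped; the supportable statement is that the SAP contradicts itself. Both ratings are collected.

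**The safety wording in SAP 2.1.2 changes no analysis.** Agreed. A reader might infer that efficacy was removed as an objective, but SAP 2.2.1, 7.2 and 9 contain a full efficacy plan. It is a clerical error.

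**Conclusion.** The point holds on three counts of unequal weight.

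- **All-patients summary:** required by Protocol 12.2, absent from the SAP and not declared as a change. This is a departure from that section, softened by the protocol's own uneven wording.
- **Interval for 12-week change or response:** the SAP commits to none, within a prior arm or overall. This is an estimation gap against the secondary objective and not a protocol departure.
- **CGI-I:** an internal SAP contradiction and a mismatch with Protocol 10.2.2. If 7.2.2 were followed with lead-in treatment start as the anchor, half to three quarters of the rated period for prior-placebo patients would be time on placebo. Those shares assume that anchor and a same-day transition into P303.

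The secondary-objective wording and the visit numbers are clerical. The textual mismatches can be read directly from the documents. No claim is made about how far results would shift, because the documents give no n or SD. The SAP should be amended before the analysis, but nothing here threatens the collected data.

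**What to change.** 1. Add an all-patients column to the efficacy tables, and align Protocol 6.3.2 and the synopsis with Protocol 12.2.
2. In SAP 9.1.1 and 9.1.2, report mean change from each baseline, and responder proportions, with 95% CIs within each prior arm and overall. Label them as uncontrolled open-label change: Protocol 8.5 relaxes limits on other medications and psychotherapy, so they do not isolate a drug effect.
3. Keep the prior-arm contrasts, labelled exploratory and not a randomised comparison within P303, since the groups are lead-in completers who qualified and chose to continue.
4. In SAP 7.2.2, 9.1.1 and 9.1.2, define two CGI-I ratings and analyse score and response separately against the P301 and P303 baselines.
5. As clerical alignment, correct SAP 2.1.2 to efficacy and renumber the visits to the P303 schedule.

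The cost is SAP wording, one extra column and one CI per efficacy table, and a second CGI-I analysis on ratings already collected. The protocol alignment is a wording change. No new data are needed.
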